Most miRNA bind to target-3'UTR and function as translational repressors most often by promoting the degradation of mRNA. Each miRNA may regulate up to 200 target genes (42). We therefore propose to correlate patterns of miRNA changes in our defined populations, with mRNA expression arrays. HMW RNA from isolated epithelial cells will be used for hybridization to Affymetrix HG-U133 Plus 2.0 microarrays. Images will be analyzed in the core facility and data will be normalized as follows: (1) per array, by dividing the raw data by the 50th percentile of all measurements; and (2) per gene, by dividing the raw data by the median expression level for all the genes across all arrays in a data set. We will determine whether up or down-regulated mRNAs are potential targets for previously identified miRNAs.

Specific Aim 3: To test the hypothesis that levels of RNA of targets in human sputum cells will differ before and after the administration of inhaled corticosteroids in asthmatics (both IA, AA). The rationale for this aim of the study is to

investigate which markers are steroid sensitive and which are steroid resistant which would provide information for therapeutic targeting in asthma.

SA3.a. We will isolate RNA targets in discrete sputum cells from induced sputum in IA and AA individuals and compare levels before and after administration of inhaled corticosteroids.

In this second phase of the study, (Phase II) we will enroll AA or IA individuals who have fit enrollment criteria for the phase I part of the study and participated in phase I of the study and were able to provide us with an acceptable sputum sample. These participants will be recontacted for participation in Phase II if they signed permission to be re-contacted. We will obtain a repeat sputum sample as baseline for the Phase II study. An inhaled corticosteroid (Fluticasone HFA 220 mcg, 1 puff twice daily) and large volume spacer will be provided. Inhalation technique and a daily diary will be reviewed. Subjects will be instructed to use Fluticasone propionate 220 mcg q puff twice daily and to record their use in a written diary. A repeat sputum sample will be obtained after 2 weeks of Fluticasone propionate use.

Sputum samples will be processed for discrete cells and RNA levels (mRNA, miRNA) will be analyzed to understand the effect of ICS use on RNA expression in discrete sputum cell populations.

Statistical Analysis:

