We were able to develop basic techniques and measurement from 10 patients in each group as initially proposed in the previous version of this protocol. We now propose to increase our enrollment from 30 to 50 subjects in each group based on the recruitment and enrollment data of about 30% of screen failures (33 subjects screen failed out of 108 total). In addition, there have been subjects who have not been able to produce sputum or provide adequate number of sputum cells for analysis (38 subjects out of 65 accrued gave adequate sputum samples). This represents about 60% success rate for sample quality. Therefore, we will need to increase our enrollment numbers to achieve an n=30 per group.

Power Analysis: Based on a similar rate of screen failures and inadequate samples, the analysis is now based on 50 patients in each group. Our group sample sizes of 50 and 50 achieve 90% power to detect a difference of 0.73 given the null hypothesis that the two-group difference is 0 and the estimated group standard deviations are 1.0 and 1.0, with a significance level (alpha) of 0.05 using a two-sided two sample t-test. We will work with [name], our biostatistician for our statistical analysis.

For ENO and EBC analyses, we will express data as means \pm SD for normally distributed variables. For variables that are not normally distributed we will use medians and the interquartile range. We will use statistical analysis including unpaired *t* tests, Kruskal-Wallis test, and regression coefficients as appropriate. P values of < 0.05 will be considered significant. Differential expression of miRNA and hierarchical clustering will be performed with the genomics core. Statistics using *t* tests or algorithms designed specifically for data mining and biochip interpretation will be used. Pathway analyses will also be performed by the genomics computational core.

Anticipated results and alternative approaches

We will continue to recruit patients with WTC exposure or with asthma based on our experience in our asthma registry or our WTC clinic, in which most people are willing and anxious to participate in any study that might help characterize their symptoms.

We plan to also submit an advertisement to the IRB for approval and to use research match (researchmatch.org) a national registry which is a secure, web-based approach as a recruitment method, and will post the advertisement.

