1. Number of Subjects: 90 (this includes the total number of subjects enrolled in phase I and II of the study that are able to produce sputum)

[Number of subjects in Phase II: 40]

The estimated number of subjects to be enrolled (signed consent, including screen failures) is 300.
2. Gender of Subjects: Men and Women (50 % each)
3. Age of Subjects: 18-80 years of age
4. Racial and Ethnic Origin: The sample population of approximately 80 participants is expected to include a distribution of subjects by race/ethnicity in relation to our local population which includes a high percentage of minority subjects (36% White, 35% Black, 50% Hispanic)
5. Inclusion Criteria:

Inclusion for the WTC population with Irritant-Induced Asthma (IA):

Patients will be recruited from the WTC EHC and will have WTC dust cloud exposure, new symptoms after 9/11, and symptoms of wheeze and shortness of breath (> 2x / week) in the 4 weeks before inclusion (persistent symptoms). We will be recruiting new subjects for phase II of the study but participants who will have completed Phase I of the study and were able to produce adequate sputum samples may also be contacted for Phase II.

Inclusion for Allergic Asthma population(AA): Patients will be recruited from the NYUBAR or advertisement and will have asthma as defined by NIH guidelines, persistent symptoms, absence of WTC dust exposure. Participants who will have completed the Phase I of the study and were able to produce adequate sputum samples may also be contacted for Phase II.

Inclusion of Control Population: Patients will be recruited from the NYUBAR and will have no respiratory symptoms, no asthma diagnosis, no WTC dust exposure, no current tobacco use, ≤ 5 p-y history of tobacco use, and normal spirometry with no bronchodilator response and negative methacholine challenge in past 6 months.

Additional inclusion criteria for individuals with IA and AA: ≥ 18 years of age, current nonsmoker, ≤ 5 pack year (p-y) history of tobacco use, spirometry in the past 6 months or on day of evaluation with a bronchodilator response of $\geq 12\%$ and 200 ml improvement in FEV₁ or a positive methacholine challenge test (decrease in FEV₁ $\geq 20\%$ (PC20) after inhalation of ≤ 16 mg/ml of methacholine), inhaled corticosteroid use in previous 1 month or more will be allowed.

Inclusion criteria for Phase II

Successfully completed Phase I

Has asthma according to Phase I diagnostic criteria

Signed consent to be re-contacted

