We will obtain epithelial cells from the lining of the nose using a technique called nasal brushing. This is a simple, nonsurgical procedure and is well tolerated by most people. We will gently brush the inside of the lateral wall of each nostril with a small, delicate, sterile brush. This procedure takes about 5 seconds for each nostril.

We also propose to correlate patterns of miRNA changes in our defined populations, with mRNA expression arrays. HMW RNA from isolated epithelial cells will be used for hybridization to Affymetrix HG-U133 Plus 2.0 microarrays. Images will be analyzed in the core facility and data will be normalized as follows: (1) per array, by dividing the raw data by the 50th percentile of all measurements; and (2) per gene, by dividing the raw data by the median expression level for all the genes across all arrays in a data set. We will determine whether up or down-regulated mRNAs are potential targets for previously identified miRNAs.

Phase II

Only subjects with Irritant asthma or Allergic asthma who have successfully completed the first phase of the study and have signed consent to be re-contacted will be recruited for the second phase of the study (Phase II). Phase II will involve two visits over a 2 week time period. For Phase II, we will first obtain sputum samples for a baseline analysis of cells. Study subjects will be provided with an inhaled corticosteroid, Fluticasone propionate HFA 220 mcg, 2 puffs twice a day (Treatment), or no treatment (No treatment). Fluticasone HFA will be provided by the study physician through the CTSI and the Bellevue Pharmacy. Treatment cases will be instructed to self administer the medication with a large volume spacer that will be provided to them. Inhaler teaching will be performed by study physician or coordinator at the time that the subject is provided the inhaler. Treatment Cases and No treatment controls will be provided a diary to record fluticasone inhaler. Treatment cases and No treatment controls will be allowed to use their usual rescue bronchodilator (albuterol) on an as needed basis. Treatment Cases and No treatment controls will return after 2 weeks for a repeat sputum induction.

2. Data Analysis and Data Monitoring:

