We will start with 10 patients in each group to develop the basic techniques and measurements. Our group sample sizes of 10 and 10 achieve 80% power to detect a difference of 1.3 given the null hypothesis that the two-group difference is 0 and the estimated group standard deviations are 1.0 and 1.0, with a significance level (alpha) of 0.05 using a two- sided two-sample t-test. Based on results from these studies we will work with [name], our biostatistician and the NYU CI Genomics core for our statistical analysis. We put in a small number of patients as this is a pilot study to develop information that will allow for a subsequent appropriate power analysis.

For ENO and EBC analyses, we will express data as means \pm SD for normally distributed variables. For variables that are not normally distributed we will use medians and the interquartile range. We will use statistical analysis including unpaired *t* tests, Kruskal-Wallis test, and regression coefficients as appropriate. P values of < 0.05 will be considered significant. Differential expression of miRNA and hierarchical clustering will be performed with the genomics core. Statistics using *t* tests or algorithms designed specifically for data mining and biochip interpretation will be used. Pathway analyses will also be performed by the genomics computational core.

For Phase II, the primary outcome is the change in TSLP gene expression in epithelial cells after 2 weeks of treatment of inhaled corticosteroid compared to no treatment. We hypothesize that a significant reduction in the gene expression will be observed in the treatment group of inhaled corticosteroid compared with the untreated group. The difference between two randomized groups will be compared using the two-group *t*-test if data are normally distributed, and the nonparametric Wilcoxon test will be used for skewed data. The effect of inhaled corticosteroids on newly identified epithelial targets (gene expression array) will also be examined. This is an exploratory goal and will be performed after cell stabilization and short-term culture cells to insure appropriate RNA quality.

Sample size and power: Group sample sizes of 15 and 15 achieve 80% power to detect a difference of 1.3SD against the null hypothesis that both group means are equal with a significance level (alpha) of 0.01 using a two-sided two-sample *t*-test assuming equal variance.

3: Data Storage and Confidentiality:

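### If Phase II is randomised, its unadjusted test of change in TSLP expression is valid but usually less efficient than adjusting for the baseline TSLP value that the outcome already requires

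*Combined protocol and SAP*

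**What the plan says.** Section III.2 (Data Analysis and Data Monitoring) states that "the primary outcome is the change in TSLP gene expression in epithelial cells after 2 weeks of treatment of inhaled corticosteroid", compared with no treatment. For the analysis it says "The difference between two randomized groups will be compared using the two-group" t-test if the data are normal, and "the nonparametric Wilcoxon test will be used for skewed data". The sample-size paragraph that follows gives 15 and 15 subjects, 80% power, a difference of 1.3 SD and a two-sided alpha of 0.01 for that t-test. No section names a covariate for Phase II. Regression is mentioned only for the ENO and EBC analyses.

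Section III.1 (Phase II) says "we will first obtain sputum samples for a baseline analysis of cells" and then "Treatment Cases and No treatment controls will return after 2 weeks for a repeat sputum induction". It does not mention TSLP. That a baseline TSLP value will exist follows from the change outcome in III.2.

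Only III.2 calls the groups randomised. Section III.1 has a treated and an untreated group but gives no allocation method. SA3.a under Specific Aim 3 will "compare levels before and after administration of inhaled corticosteroids", with no untreated group. On numbers, section II.1 has "Number of subjects in Phase II: 40" against 15 + 15 in III.2, and the Statistical Analysis section reports that "38 subjects out of 65 accrued gave adequate sputum samples".

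**The concern.** Every subject who contributes a change in TSLP also contributes a baseline TSLP value, and the planned test uses that value only by subtracting it. Subtraction assumes that a subject who starts one unit higher will, untreated, finish one unit higher. If the true slope is shallower, the change score carries baseline noise that adjustment would remove.

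The stake is the precision of the Phase II primary comparison. That comparison is small and tested at a strict alpha, and it needs two usable sputum samples per subject when adequate sputum is a known difficulty. Adjustment uses samples already planned.

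**Working it through.** **Inputs.** From III.2: n = 15 per arm, two-sided alpha 0.01, difference 1.3 SD, equal-variance t-test. Not in the documents, so assumed: r; the week-2/baseline SD ratio k; the expression scale; and what the 1.3 SD is the SD of. I read it as the SD of the change, because the outcome is the change.

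**1. The plan's own figure.** The noncentrality is 1.3 × √(15/2) = 3.56 with 28 df. Exact power is 78.0%. At 15 per arm, 80% needs 1.327 SD, which rounds to the stated 1.3. At exactly 1.3 SD, 80% needs 16 per arm. The stated figure therefore reproduces with rounding.

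**2. Why adjustment helps.** Set the baseline SD to 1 and the week-2 SD to k.
- Variance of change: 1 + k² − 2rk.
- ANCOVA residual variance: k²(1 − r²).
- Difference: 1 − 2rk + r²k² = (1 − rk)².

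The best slope is rk, that is r × SD(week 2)/SD(baseline). Before any small-sample cost the change score is never better, and it ties only when rk = 1. The slope is below 1 unless k is at least 1/r, so with equal SDs it is below 1 at every r < 1. With k = 1 the variance ratio is (1 − r²)/[2(1 − r)] = (1 + r)/2.

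**3. The small-sample cost.** ANCOVA has 2n − 3 = 27 df. Chance baseline imbalance inflates the variance on average by 1 + 1/(2n − 4) = 1 + 1/26 = 1.038. At r = 0.5 the ratio is 0.75 × 1.038 = 0.779, the standardised effect becomes 1.3/√0.779 = 1.47, and power is 88.6%.

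**4. Power (%), 1.3 SD of change, two-sided alpha 0.01, averaged over chance baseline imbalance.**

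| n per arm, k | Unadjusted | r = 0.3 | 0.5 | 0.7 | 0.8 | 0.9 | 0.95 |
|---|---|---|---|---|---|---|---|
| 12, k = 1 | 64.3 | 83.4 | 76.7 | 70.2 | 67.1 | 64.2 | 62.8 |
| 15, k = 1 | 78.0 | 93.1 | 88.6 | 83.6 | 81.0 | 78.4 | 77.2 |
| 20, k = 1 | 91.2 | 98.7 | 97.1 | 94.7 | 93.3 | 91.8 | 91.0 |
| 15, k = 1.2 | 78.0 | 88.0 | 82.5 | 77.6 | 76.0 | 77.0 | 82.2 |
| 15, k = 0.9 | 78.0 | 95.7 | 92.4 | 88.5 | 86.7 | 85.6 | 86.6 |

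Twenty per arm is 40/2 from II.1. Twelve is an assumed loss of samples.

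**5. Where ANCOVA loses.** With equal SDs and 15 per arm, the break-even r is about 0.92. The small loss above it comes from the lost degree of freedom and chance imbalance, since the slope is still below 1. With k = 1.2 there is a loss for r of about 0.69 to 0.91, that is slopes of about 0.83 to 1.09. The largest loss, at slope 1, is 3.6, 2.9, 2.1 and 1.0 points at 9, 12, 15 and 20 per arm. Nine per arm is 15 × 38/65 = 8.8, rounded.

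**6. Other reading of 1.3 SD.** If it is the SD of the expression level (k = 1, n = 15), unadjusted against ANCOVA is 60.0 v 80.5% at r = 0.3, 78.0 v 88.6% at 0.5 and 95.9 v 97.7% at 0.7.

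**7. Validity.** In simulation with normal data at alpha 0.01, both tests rejected a true null in 0.9 to 1.0% of trials at every r tried.

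**8. Skewed branch (simulation, n = 15, equal SDs, assumed shapes).** If log values are normal, Wilcoxon on log change has about 75% power against 93 to 77% for log-scale ANCOVA. If log values are themselves still log-normal, Wilcoxon has about 94 to 95% against 92, 91, 89 and 85% for ANCOVA at r = 0.3, 0.5, 0.7 and 0.9, so parametric ANCOVA loses throughout. A rank-based ANCOVA (ranked change on group and ranked baseline) beat plain Wilcoxon at every r and shape simulated, with null rejection of about 1% in the two null cells run.

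**The case against.** The strongest reply is that the plan names a test, a fallback for skewed data and a sample size for that same test, and that all of these are legitimate. Preferring ANCOVA is a refinement whose size depends on r, the SD ratio and the scale, none of which the documents supply. Nothing in them says which r is plausible for TSLP in sputum epithelial cells. This stands, and it is why the gain is given as a range.

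A second objection also stands. Making parametric ANCOVA primary in every case would remove the plan's protection against skew, and step 8 shows that this can cost power at every r. Heavy tails alone are enough: with symmetric t data on 3 df, Wilcoxon has 88% against 83% for ANCOVA at r = 0.9. The fix therefore keeps the plan's normal/skewed split. A log scale also needs a rule for undetectable TSLP, whose log is undefined.

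Third, the point depends on the design. One word in III.2 carries the randomisation, and SA3.a describes no untreated group. That question comes first.

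None of this removes the core point: if the groups are randomised, the planned comparison leaves unused a baseline value that it already needs.

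**Conclusion.** The point holds as a cheap improvement. With equal visit SDs and 15 per arm, ANCOVA changes power from 78% to between 93% (r = 0.3) and 77% (r = 0.95). It loses only in a band around slope 1 or at very high r, by about 2 points at most at 15 per arm. These figures assume 1.3 SD of change, a roughly linear relation with baseline on the chosen scale, and all subjects analysable.

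A reader might infer three stronger things that the documents do not support.
- **The planned test is wrong or biased.** Under randomisation it keeps its error rate. Both analyses share the further assumption that missing or inadequate repeat sputum does not depend on arm and outcome.
- **Adjustment always wins.** It does not, as step 5 shows.
- **Section III.1 itself specifies a baseline TSLP measurement.** It refers only to a baseline analysis of cells; the TSLP value is implied by the outcome in III.2.

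**What to change.** Reconcile SA3.a, III.1 and III.2 on whether Phase II is a randomised two-group comparison. If it is not, stop here: the fix does not apply.

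If it is:
- State the expression scale in advance (for example log), with a rule for undetectable values.
- If approximately normal: ANCOVA of week-2 TSLP on randomised group and baseline TSLP, both on the chosen scale, reporting the adjusted difference and its CI.
- If skewed: a rank-based ANCOVA (ranked change on group and ranked baseline) in place of the plain Wilcoxon.
- Keep the planned t-test or Wilcoxon on change as a sensitivity analysis.

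The cost is a few sentences of analysis text and one degree of freedom, with no new samples or visits. The downside in the t-test branch is about 1 to 4 power points if the slope is near 1, as set out in step 5.

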AA: These patients will be recruited from the NYUBAR (N = 30) and advertising and will have asthma as defined by NIH guidelines (51), persistent symptoms, and absence of WTC dust exposure.

Control: These patients will be recruited from the NYUBAR (N = 30) and advertising and will have no respiratory sx, no asthma diagnosis, no WTC dust exposure. Additional appropriate inclusion and exclusion criteria will be developed for each group including tobacco use, other lung disease, timing of inhaled corticosteroids etc.

The study will entail two to three visits. On visit 1 (V1) all individuals will sign informed consent to participate in the study under an NYU IRB approved protocol. A questionnaire will be completed with standardized questions that include information on WTC exposures, demographics, presence and severity of respiratory symptoms, tobacco history and past medical history. Individuals will undergo spirometry with inhaled bronchodilator. Individuals will undergo methacholine challenge test (visit 1a) if they have normal spirometry or no bronchial hyperresponsiveness. On visit 2, individuals will return to undergo ENO, EBC and spirometry with pre and post bronchodilator maneuvers and induced sputum. Blood will be obtained for CBC with differential cell count, and assessment of total IgE and allergen-specific IgE. Blood will also be stored for future analysis of inflammatory markers. Based on our experience, we have had individuals unable to produce enough sputum and thus yield too small a number of cells. These individuals are excluded from data analysis. In addition, we also have subjects who are able to produce sputum and return for repeat sputum testing.

SA1.b We will measure biomarkers of inflammation using noninvasive techniques for exhaled nitric oxide (ENO) and 8-isoprostanate from exhaled breath condensate (EBC) in WTC IA, AA and controls.

We will use the handheld NIOX MINO® to measure ENO (Aerocrine, Sweden) (17, 18, 20, 52). The NIOX MINO® fulfills the ATS recommendations and provides reliable readings and is portable and we have experience with it (53). Most healthy individuals have ENO levels in the range of 5-35 ppb (some variation with age, gender, race/ethnicity) (54). Individuals with asthma have ENO levels that can range from 25-80 ppb and even higher (18, 61, 62).

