Care will be taken to ensure confidentiality. Research records will be held in locked cabinets or secure storage rooms. All transmission of data to the coordinating center for analysis will be by study ID code only.

Sample specimens will be stored for up to 10 years for future use or until the end of the study. Participants will be able to decide if they want any of their specimens stored for research done at a later time.

IV. Risk/Benefit Assessment

1. Risk: Minimal Risk

Spirometry, ENO, IOS and EBC.

Participation in these studies will pose minimal risk of physical or psychological harm. Spirometry, impedance oscillometry, ENO and exhaled breath condensate collection are minimally invasive.

Methacholine testing: MCT has been performed with no serious side effects. Participants may develop transient side effects such as cough, mild dyspnea, and chest tightness although many experience no symptoms. Inhaled methacholine can cause bronchoconstriction and safety of each subject is considered prior to testing. A physician and the medical director of the pulmonary lab are trained to treat acute bronchospasm, including appropriate use of resuscitation equipment, and a physician is present during the procedure. Our pulmonary function lab in Bellevue Hospital is well trained in performing MCT in the clinical and research setting. If bronchospasm occurs appropriate medications will be administered as per the lab protocol (oxygen, nebulizers, subcutaneous epinephrine). If a participant in the study develops an acute asthma episode during any part of this procedure, the procedure will be stopped and albuterol will be administered to improve breathing. The bronchodilator will be provided by a physician involved in the study and the participant will be monitored until their breathing has returned to its baseline.

For all women of childbearing ability, a pregnancy test will be performed before the methacholine challenge study. Pregnant subjects will be excluded from the study.

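### Read as study-wide, the pregnancy exclusion has no described check at Phase II entry, nor in Phase I for asthmatic women who qualify without a methacholine challenge

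*Combined protocol and SAP*

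**What the plan says.** All references are to the combined protocol and SAP.

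- **Test and exclusion.** Pregnancy is mentioned once in the visible text, in section IV.1 under Methacholine testing: "a pregnancy test will be performed before the methacholine challenge study. Pregnant subjects will be excluded from the study".
- **Who is challenged.** Research Design and Methods, SA1.a: "Individuals will undergo methacholine challenge test (visit 1a) if they have normal spirometry or no bronchial hyperresponsiveness".
- **How asthmatics qualify.** Section II.5 accepts either of two routes for the irritant (IA) and allergic (AA) groups. One is "spirometry in the past 6 months or on day of evaluation with a bronchodilator response" above a stated threshold; the other is a positive methacholine challenge.
- **How controls qualify.** Section II.5 requires "normal spirometry with no bronchodilator response and negative methacholine challenge in past 6 months".
- **Exclusion list.** Section II.6 has seven items, and pregnancy is not one of them. Section II.7 says that vulnerable subjects will not take part, without defining the term.
- **Phase II.** SA3.a: "These participants will be recontacted for participation in Phase II if they signed permission to be re-contacted", then "We will obtain a repeat sputum sample as baseline for the Phase II study", then fluticasone. Section III.1 gives the same order and adds an untreated group. The Phase II criteria in II.5 are completion of Phase I, asthma by the Phase I definition, and consent to re-contact.
- **History.** The visit 1 questionnaire in SA1.a covers "tobacco history and past medical history".

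**The concern.** The test is tied to one procedure, while the exclusion is worded for the study. Where that procedure is not done, the visible text gives staff no way to apply the exclusion. A woman with an unrecognised pregnancy could pass every described step and still undergo sputum induction, or take two weeks of inhaled fluticasone that IV.1 itself describes as high dose.

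The plan's own reasoning makes the omission hard to explain. Section IV.1 names bronchoconstriction as the hazard of methacholine. It names the same hazard for hypertonic saline in asthmatics and refers back to the methacholine rescue procedure, yet a pregnancy test is described before only one of the two.

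At stake are eligibility and safety. No estimate, test or power figure depends on it.

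**Working it through.** No formula in the plan bears on this, so the check sets the eligibility, procedure and risk text side by side.

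**1. Who reaches the only described test?**

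| Group | Route through the plan | Pregnancy test described |
|---|---|---|
| Controls | Must have normal spirometry, so they meet the SA1.a trigger | Yes, unless a challenge from the past 6 months is accepted in place of the in-study one |
| IA/AA, normal spirometry | Meet the trigger | Yes |
| IA/AA, abnormal spirometry, qualifying bronchodilator response | Eligible under II.5 without a challenge; trigger not plainly met | None |
| Phase II, challenged in Phase I | Re-contact, sputum, fluticasone or no treatment, sputum | Once, in Phase I; no re-test |
| Phase II, not challenged in Phase I | Same | None at any point |

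**2. Do the entry criteria close the gap?** The II.6 items are current smoking, pulmonary disease, cardiac disease, inability to perform the manoeuvres, recent upper respiratory infection, low FEV1 and recent oral corticosteroids. That is 7 items, 0 on pregnancy. Of the 3 Phase II criteria, 0 mention pregnancy and 0 limit the time since Phase I. The plan gives no interval between the phases, so a Phase I result may or may not still be current.

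**3. What follows an unchecked Phase II entry?** There are two sputum inductions (baseline and week 2), and no test is described before either: 2 of 2. In the treated group there is also fluticasone. SA3.a gives "Fluticasone HFA 220 mcg, 1 puff twice daily"; III.1 gives two puffs twice a day.

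- SA3.a: 220 × 1 × 2 = 440 mcg/day; × 14 days = 6,160 mcg.
- III.1: 220 × 2 × 2 = 880 mcg/day; × 14 days = 12,320 mcg.

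The two-fold range comes from a separate inconsistency in dosing. It describes exposure and does not measure harm.

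**4. How many women?** Section II gives 40 subjects in Phase II and half women overall. If that split carried into Phase II, 40 × 0.5 = 20 women, aged 18 to 80, of whom an unknown part could become pregnant. In Phase I, the Background says that most symptomatic patients in the WTC clinic have normal screening spirometry. The Preliminary data report 6% of the clinic population with obstruction and 20% with reduced lung volume. This suggests that few IA women escape the challenge, but these are clinic figures and not enrolled subjects, and nothing comparable is given for AA. The number of unrecognised pregnancies cannot be estimated from the documents.

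**The case against.** **Scope of the sentence.** The exclusion closes the methacholine paragraph, straight after a sentence ending on the methacholine challenge study, so it may mean that procedure only. Test and exclusion would then match. This stands as a real alternative. Against it, the same paragraph elsewhere uses the word study for the whole project, and II.7 fits a wider exclusion if pregnancy counts as a vulnerability, which the plan does not say. On the narrow reading the plan still does not state expressly whether pregnant women may have sputum induction or Phase II treatment.

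**Unseen text.** The consent forms, including the separate Phase II form, and a short stretch of text before the consent section were not available. A test described there cannot be ruled out. What can be said is that the visible eligibility, procedure and risk sections describe none.

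**Reach.** A reader might infer that every woman entering Phase II is untested. The documents do not support that: those challenged in Phase I should have been tested then and lack only a re-test. Nor are controls a general gap, since they normally meet the trigger. The trigger's second limb, on hyperresponsiveness, is undefined, so some bronchodilator responders might be challenged anyway. The visit 1 history could reveal a known pregnancy, which leaves unrecognised pregnancy as the issue; no such questionnaire is described for Phase II.

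**Harm.** A reader might also infer that induction or fluticasone endangers a pregnancy. The documents show no such contraindication. Section IV.1 rates the course as minimal risk and notes that it is an approved asthma treatment, and II.5 allows existing inhaled corticosteroid use. That stands in full.

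**Conclusion.** The concern holds in a limited form. If the exclusion is study-wide, the visible plan describes no check at Phase II entry: 0 tests before 2 of 2 inductions and before the 14-day course, and no limit on time since Phase I. Nor does it describe one in Phase I for the probably small group of asthmatic women with abnormal spirometry who qualify on bronchodilator response alone. The Phase II part is the firmer of the two, because it does not turn on how the challenge trigger is read.

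The conclusion assumes the study-wide reading and that the unseen text contains no further test. If the first assumption fails, the point becomes one of unclear scope; if the second fails, it becomes one of placing the test where staff will look for it. It is a cheap improvement to eligibility and safety wording, held with medium confidence. It is not a statistical defect and not a claim of fetal harm.

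**What to change.** 1. List pregnancy among the exclusion criteria in II.6.
2. In the Phase II criteria (II.5) and procedures (SA3.a and III.1), require a pregnancy test for women of childbearing ability at the baseline visit, before sputum induction and before fluticasone is dispensed.
3. At Phase I screening, test those who will have no in-study methacholine challenge, including any control whose challenge from the past 6 months is accepted instead. Keep the existing test before the challenge for everyone else.
4. If the exclusion was meant for methacholine only, say so in IV.1 and state whether pregnant women may have sputum induction and Phase II treatment.

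The cost is some protocol wording and a few more tests of a kind the study already uses: about 20 at most at Phase II baseline if half of the 40 subjects are women, plus the unchallenged women in Phase I. Sample size, power and analysis do not change.
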